14.1 Phase I

14.1.1 Primary endpoint

The main objective of the study is to establish the maximum tolerated dosage (MTD) of hu3F8-BsAb. The MTD will be defined as the dose whose toxicity rate does not exceed an acceptable threshold of toxicity of 15%. DLT is defined in Section 9.1. In the first stage, the trial will accrue 1 patient per dose until the first \geq Grade 2 related toxicity (except for Grade 2 sinus bradycardia, sinus tachycardia, fever, nausea, vomiting, diarrhea, urticaria, headache, paresthesia, electrolyte disturbances, pain) is encountered. The subsequent dose allocation will follow the CRM. CRM assumes a simple model for the probability of a DLT as a function of dose, and uses the occurrence of toxicities in the patients enrolled in the trial to sequentially determine which dose to administer to a new patient. Patients will be assigned at each dose one at a time. New subjects will be allocated a dose as suggested by the CRM algorithm based on the toxicities of previously accrued patients. If the DLT data are not available for the previously accrued 1 or 2 patients, the CRM will proceed with the dose as calculated with available toxicities/data, however if there are 3 enrolled patients with incomplete /outstanding DLT data the accrual will be paused. DLT data from at most 2 patients can be pending but no more than 2 patients are allowed to have DLT data not complete. To protect patient safety, a dose escalation of more than

one dose level is not permitted. If no DLT is observed, the RP2D will be determined as a minimum dose that gives the highest hu3F8-BsAb serum levels based on the PK data.

We will examine 12 dose levels as described in Table 4 (Section 9.1). Our initial estimates of DLT probabilities are: 0.001, 0.005, 0.01, 0.025, 0.05, 0.075, 0.10, 0.15, 0.25, 0.35, 0.45, 0.50 for doses 1-12, respectively. Thus, our a priori belief is that dose level 8 is the MTD. The starting dose level will be dose level 1. We assume that the dose-toxicity follows a hyperbolic tangent model P(DLT=yes at dose d)=((tanh d+1)/2)^a, where a is the unknown parameter that we need to estimate in order to determine which dose is the MTD. A value of a=1.0 indicates that our prior beliefs were correct; while a value of a less than (greater than) 1.0 indicates that the combinations are more (less) toxic than believed. To reflect the uncertainty in our prior probability estimates, we assume it follows an exponential distribution (prior distribution) with mean 1.0. Dose escalation will be guided by the model after the occurrence of the first DLT. At that time, the above initial estimates of DLT might be revisited before model initiation to reflect the current knowledge on the safety profile and dose levels based on the observed data.

We will enroll 30 evaluable patients; We expect to enroll 10-15 patients/year, and it is expected that the trial will be open to accrual for 36 months. All patients who are enrolled in the study and receive at least one dose of hu3F8-BsAb are considered evaluable for toxicity. Additional subjects will be enrolled to replace any subjects who are enrolled, but do not receive any treatment. An amendment in the dose levels was done after the inclusion of 5 patients to dose levels 1 to 4; however, the modifications only impacted dose level 5 and higher, therefore the 5 first patients are still part of the CRM and will be analyzed as planned. The amendment does not modify the operating characteristics of the CRM.

14.1.1.1 Operating characteristics

Through 1000 simulated trials with the above parameters we expect the method to behave in the following way, assuming three different hypothetical scenarios for the true toxicity rates at each dose level:

Dose levels	1	2	3	4	5	6	7	8	9	10	11	12
Scenario 1	0.01	0.02	0.05	0.15	0.25	0.35	0.35	0.40	0.45	0.50	0.50	0.50
Scenario 2	0.001	0.005	0.01	0.02	0.03	0.05	0.10	0.15	0.25	0.35	0.45	0.60
Scenario 3	0.001	0.005	0.01	0.02	0.03	0.04	0.05	0.06	0.07	0.08	0.09	0.10

Table 9Hypothetical True Toxicity Rates

Dose levels	1	2	3	4	5	6	7	8	9	10	11	12
Scenario 1	0.1	1.5	15.2	47.2	26.3	5.4	3.2	0.9	0.2	0.0	0.0	0.0
Scenario 2	0.0	0.0	0.0	0.2	1.0	5.4	18.5	42.5	26.3	5.5	0.5	0.1
Scenario 3	0.0	0.0	0.0	0.2	0.4	1.2	2.9	10.7	14.7	15.7	14.4	39.8

Table 10Percent of simulated trials that selected each dose under each scenario

Table 11Percent of patients treated at each dose under each scenario

Dose levels	1	2	3	4	5	6	7	8	9	10	11	12
Scenario 1	3.9	7.2	19.5	30.8	20.8	8.7	5.1	2.9	0.8	0.2	0.06	0.0
Scenario 2	3.4	4.3	6.7	6.6	7.8	9.9	14.7	23.2	16.3	5.3	1.6	0.2
Scenario 3	3.4	4.4	6.7	6.5	6.9	7.2	8.6	11.8	11.9	9.8	8.7	14.0

Table 12Average toxicities across trials at each dose

Dose levels	1	2	3	4	5	6	7	8	9	10	11	12
Scenario 1	0.0	0.0	0.3	1.4	1.5	1.0	0.5	0.3	0.1	0.0	0.0	0.0
Scenario 2	0.0	0.0	0.0	0.0	0.1	0.1	0.4	1.0	1.2	0.6	0.2	0.0
Scenario 3	0.0	0.0	0.0	0.0	0.1	0.1	0.1	0.2	0.2	0.2	0.2	0.4

14.1.1.2 Dose Allocation in CRDB Section for the Protocol

Patient Registration and the CRDB CRM module are run independently. Once new patients are registered, the CRDB CRM module can be run by members of the protocol research team to generate the CRM report which includes the recommended dose level for the newly registered patient.

During the first stage, one patient is accrued at a time starting at the first dose level and followed for DLT before the next patient is accrued. Patients must be followed for 28 days to determine if they had a DLT. If no DLT is seen, then the next patient is accrued at the next higher dose level. This process

will continue until a DLT is seen. Once a DLT is seen, the study team should notify the CRDB Helpline and the study statistician in order to have the protocol switched to the model-based stage. The dose level of subsequent patients will be assigned by the CRM module. The CRM program uses information specified in the Biostatistics section of the protocol and the summarized toxicity data of previously treated patients as displayed in the CRM report to determine the next dose level to which the patient will be assigned. Only eligible and evaluable patients are used in determining the next dose level. Patients accrued during the model-based stage must also be followed for 28 days to determine if they had a DLT. Since the protocol allows 2 patients to have incomplete toxicity data, then the CRM algorithm can still generate a dose assignment even if toxicity/DLT data are missing for up to 2 patients who were last registered to the protocol. If toxicity data is missing on more than 2 patients or other required data is missing, the CRM module will not provide the next dose assignment and a message indicating missing data will be generated.

The CRM report includes summary and detailed toxicity information and the recommended next dose level (determined by the CRM program). The report will normally be generated by the CRC; however other members of the research team can be given access to run the CRM module. The dose level for new patients is not automatically saved. The PI must check the report to determine if all toxicity data are correct and up-to-date. If the data are correct, the PI will acknowledge this and sign the last page of the report which displays the recommended dose assignment. The last page of the report also contains space to fill in the MRN and name of the newly registered patient who is to receive this dose assignment. The CRC will enter the dose level in CTMS after a patient is registered.

If any data are incomplete or incorrect, the PI will inform the CRC. The CRC will correct the data and indicate to the PI when this is done. The CRDB CRM module will be run again to determine the next patient's dose level. The report will be generated and the PI will be notified to approve the assignment. The dose level will then be entered into CTMS.

Although both children and adults are eligible for enrollment on this study, we do not anticipate any significant differences in target specific toxicity between adults and children based on our experience of over 780 children under age 12 and over 100 patients over age 12 (including >50 over age 18) in the past 20 years with m3F8 and hu3F8. Additionally, there are no reported significant differences in the toxicity of blinatumomab in children compared to adults; 65 thus children and adults will be enrolled and evaluated simultaneously on each dose level.

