4.1 Design

4.1.1 Phase I

Initially the phase I study will follow a dose-escalation escalation schema with 1 patient assigned per dose until the first \geq Grade 2 toxicity (except for Grade 2 sinus bradycardia, sinus tachycardia, urticaria, fever, nausea, vomiting, diarrhea, urticaria, headache, paresthesia, electrolyte disturbances, pain) is observed, then the subsequent dose allocation will follow the Continual Reassessment Method (CRM).^{75,76}a. Eligible patients will include relapsed or refractory NB, osteosarcoma, and GD2 (+) solid tumors. In each cycle, hu3F8-BsAb is given on Days 1 and 8. PK is assessed by blood draws. Patients are monitored for DLT until Day 28. Patients with DLT will come off treatment. HAHA titer will be measured after each cycle. Extent of disease evaluation will be performed after the second dose of cycle 2 and cycle 4, then every 3 months thereafter. A total of 4 cycles will be given. If patients experience no life-threatening toxicity clearly attributable to hu3F8-BsAb, do not develop progression of disease (PD) and continue to meet all eligibility criteria, they have the option of receiving additional cycles up to 2 years from the start of hu3F8-BsAb treatment. Patients may continue therapy beyond 4 cycles even if they achieve remission, see study design Figure 6.

The duration of each subsequent cycle is 28 days with hu3F8-BsAb being given on Days 1 and 8. MTD is defined as a maximum dose level at which ≤ 1 of 6 patients experiencing DLT. The RP2D will be decided based on the safety data in the phase I and can be MTD or lower. If MTD is not reached, RP2D may be determined on the basis of PK studies. If no DLT is observed, the RP2D will be determined as a minimum dose that gives the highest hu3F8-BsAb serum levels based on the PK data. For example, the RP2D of hu3F8 monoclonal antibody was decided as 9 mg/kg/cycle because the serum hu3F8 levels reached a plateau beyond 8.4 mg/kg/cycle with no DLT (see Section 3.2.3). After cycle 2, intra-patient dose escalation will be permitted i.e. patients can receive the highest dose that has been evaluated and proven safe by DLT assessment.

[figure not shown]

Figure 6 Study design

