9.1.2 Dose-Escalation Plan and Dose Limiting Toxicity (DLT)

9.1.2.1 Dose-Escalation Plan

This is a Phase I trial to determine the MTD of hu3F8-BsAb that leads to DLT in approximately 15% of patients. Hu3F8-BsAb is dosed based on body weight (BW) rather than body surface area (BSA). Unlike chemotherapy for which clearance ultimately depends upon cardiac output which is dependent upon BSA, antibody distribution and clearance depend on total blood volume which is determined not by BSA, but by BW. Dose escalation will start at dose level 1, 0.0045 mcg/kg/dose (0.009 mcg/kg/cycle). Dose-escalation will be performed in two stages. In the first stage, the trial will accrue 1 patient per dose until the first \geq Grade 2 toxicity (except for Grade 2 sinus bradycardia, sinus tachycardia, fever, nausea, vomiting, diarrhea, urticaria, headache, paresthesia, electrolyte disturbances, pain) is encountered. The subsequent dose allocation will follow the Continual Reassessment Method (CRM). CRM assumes a simple model for the probability of a DLT as a function of dose, and uses the occurrence of toxicities in the patients enrolled in the trial to sequentially determine which dose to administer to a new patient. Patients will be assigned at each dose one at a time. New subjects will be allocated a dose as suggested by the CRM algorithm based on the toxicities of previously accrued patients. If DLT data are not available for the previously accrued 1 or 2 patients, the CRM will proceed with the dose as calculated with available toxicities/data, however if there are 3 enrolled patients with incomplete /outstanding DLT data, accrual will be paused. DLT data from at most 2 patients can be pending but no more than 2 patients are allowed to have incomplete DLT data. To protect patient safety, a dose escalation of more than one dose level is not permitted. We will examine 12 dose levels. (Table 4) Our initial estimates of DLT probabilities are: 0.001, 0.005, 0.01, 0.025, 0.05, 0.075, 0.10, 0.15, 0.25, 0.35, 0.45, 0.50 for doses 1-12, respectively. Thus, our a priori belief is that dose level 8 is the MTD. We assume that the dose- toxicity follows a hyperbolic tangent model P(DLT=yes at dose d)=($(\tanh d+1)/2$)^a, where a is the unknown parameter that we need to estimate in order to determine which dose is the MTD.A value of a=1.0 indicate that our prior beliefs were correct; while a value of a less than (greater than) 1.0 indicates that the combinations are more (less) toxic than believed. To reflect the uncertainty in our prior probability estimates, we assume it follows an exponential distribution (prior distribution) with mean 1.0. Dose escalation will be guided by the model after the occurrence of the first DLT. At that time, the above initial estimates of DLT might be revisited before model initiation to reflect the current knowledge on the safety profile and dose levels based on the observed data. We will enroll 30 evaluable patients. All patients who are enrolled in the study and receive their assigned dose are considered evaluable for toxicity. Additional subjects will be enrolled to replace any subjects who are enrolled, but do not receive treatment. In the

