
unlikely event that patient stops the drug due to HAHA before completing the first cycle, this patient will be considered inevaluable and will be replaced. If life-threatening toxicity occurs in any patient, further accrual at that dosage will be stopped pending review by the Principal Investigator (PI) or Co-PI. Toxicity at each dosage level is evaluated during the 28 days following the first dose of hu3F8-BsAb. No more than two patients will receive their first dose of hu3F8-BsAb within a 24 hour period. If no DLT is observed up to dose level 12 during the initial patient per dose escalation (e.g. no MTD), the RP2D will be determined as a minimum dose that gives the highest hu3F8-BsAb serum levels based on the PK data.

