9.1.2.2 Dose Limiting Toxicities

Toxicity will be monitored using CTCAE version 4.0. DLT only during cycle 1, i.e. Days 1 through 28. Allowance will be made for the expected toxicities of hu3F8 from which hu3F8-BsAb was derived. (See Section 11.2). As stated above, in the first stage (1 patient per dose-level) dose-escalation will be performed until \geq Grade 2 related toxicity (except for Grade 2 sinus bradycardia, sinus tachycardia, urticaria, fever, nausea, vomiting, diarrhea, urticaria, headache, paresthesia, electrolyte disturbances, pain) is encountered, then the subsequent dose allocation will follow the CRM.^{75,76}

During the CRM phase, any \geq Grade 3 toxicity attributable to hu3F8-BsAb will be considered doselimiting with the following exceptions:

- Grade 3 cytokine release syndrome (CRS) improving to ≤Grade 1 CRS within ≤72 hours after starting systemic steroids (See Section 11.3 for a grading system and algorithm)
- Grade 3 pain improving to \leq Grade 2 within \leq 72 hours of its onset. Grade 3 pain associated with myalgia is an expected clinical toxicity associated with cytokine release syndrome (CRS).
- Grade 3 neutropenia or anemia
- Grade 3 thrombocytopenia without clinically significant bleeding.
- Grade 4 lymphopenia
- Grade 3 elevations of AST, ALT if they return to <Grade 3 by day 28
- Catheter related infections
- DLT of hypertension is defined as persistent hypertension higher than 99th percentile for >48 hours.

The following Grade 3 toxicities are related to infusion of monoclonal antibodies and will not be considered DLT if they resolve to <Grade 3 within 24 hours:

- Allergic reactions controlled with supportive care measures
- Vasovagal reaction
- Sinus bradycardia

- Sinus tachycardia
- Urticaria (improved to at least Grade 2)
- Fever

The following Grade 3 toxicities will not be considered a DLT if they resolve within 48 hours:

- Nausea
- Vomiting
- Diarrhea
- Peripheral neuropathy (paresthesia)
- Electrolyte disturbances

In all other cases, DLT is defined as Grade 3 or greater toxicities occurring during cycle 1 with the exception of toxicities clearly related to disease activity or co-interventions.

9.1.3 Criteria for continuing on therapy beyond cycle 1.

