13 CRITERIA FOR REMOVAL FROM STUDY

- **13.1** Patients come off treatment if there is PD at any time. Best clinical judgment will be used to determine whether a patient must undergo tests between cycles to make sure disease is not progressing. Patients are followed for toxicities for 30 days from last treatment.
- 13.2 Patients come off treatment if they have DLT (during cycle 1 of phase I) or life-threatening toxicity clearly attributable to hu3F8-BsAb. Patients in the first stage of phase I (one patient per dose level cohort) who experience ≤ grade 2 toxicity, will not come off treatment but can continue at the same dose if they do not experience DLT and if toxicity subsides to <grade 2 within 35 days of dose 1 of Hu3F8-BsAb.

- **13.3** Patients who become pregnant during the study must be withdrawn from treatment
- **13.4** The investigators will make every reasonable effort to keep each patient in the study until all planned treatments and assessments have been performed. The investigators may discontinue study drug treatment for the following reasons:
 - Adverse events, including unacceptable toxicity or exacerbation of underlying disease, associated with study drug administration and necessitating discontinuation of treatment. Patients who are coming off treatment due to adverse events will be treated and followed according to established, acceptable medical practice. All pertinent information concerning the outcome of such treatment will be entered in the MSKCC institutional Clinical Research Database (CRBD). Patients will be followed until resolution or stabilization of the adverse event.

13.5 Off Study Criteria:

- Thirty days after the last dose of study drug for patients coming off treatment due to DP
- For patients coming off treatment due to adverse events, patients will be followed until the date the event returns to baseline or <Grade 3 (whichever is higher) or the date patients start another treatment, whichever is earlier.
- Death
- Lost to follow-up
- Withdrawal of consent. The patient's desire to withdraw from the study may occur at any time. The investigator should carefully consider whether the patient's withdrawal of consent is due to an adverse event, and if so, record the adverse event as the reason for withdrawal.
- Withdrawal by the physician for clinical reasons not related to study drug treatment in the absence of an adverse event.

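### The protocol and SAP give two different events for ending one-patient-per-level escalation and starting the CRM, leave the stage 1 waiting rule unclear, and print a Table 11 that the rule in protocol 14.1.1.2 does not produce

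*Protocol*

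**What the plan says.** **Trigger: first non-excepted Grade 2 or higher toxicity.** Protocol 4.1.1, 9.1.2.1, 9.1.2.2 and the opening of 14.1.1 use this event, as do SAP 2.1.1.1, 2.1.1.3 and 2.1.1.5. Section 9.1.2.2 says that "in the first stage (1 patient per dose-level) dose-escalation will be performed until" a related toxicity of at least Grade 2 outside a list of exceptions is met. The CRM then takes over.

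**Trigger: first DLT.** The later text of protocol 9.1.2.1, the model paragraph of 14.1.1, and 14.1.1.2 use this event, as do the closing text of SAP 2.1.1.3 and SAP 2.1.1.4. Section 14.1.1.2 says that stage 1 "will continue until a DLT is seen. Once a DLT is seen, the study team should notify the CRDB Helpline". The end of 9.1.2.1 fits this version, since it provides for the case "If no DLT is observed up to dose level 12 during the initial patient per dose escalation".

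**Waiting.** In 14.1.1.2, stage 1 means that "one patient is accrued at a time starting at the first dose level and followed for DLT before the next patient is accrued", with 28 days of follow-up. Sections 9.1.2.1 and 14.1.1 mention no such wait. They say that with one or two patients' DLT data outstanding "the CRM will proceed with the dose as calculated with available toxicities/data", and that accrual pauses at three.

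**Step limit.** "To protect patient safety, a dose escalation of more than one dose level is not permitted". The text does not say whether the step is counted from the last assigned level or from the highest level with complete data.

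**Simulation.** Section 14.1.1.1 reports 1,000 trials run under the parameters given before it. It states no trigger, pending-data rule, accrual rate or Grade 2 rate.

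**The concern.** The two triggers are different events. Protocol 13.2 says that a stage 1 patient with toxicity up to Grade 2 "will not come off treatment but can continue at the same dose if they do not experience DLT", so a Grade 2 event and a DLT are kept apart. SAP section 7 rewrites the MTD definition and the set evaluable for DLT but leaves the trigger open. Both versions are printed in full, so redaction does not explain the conflict.

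The conflict matters after a Grade 2 event without a DLT. One version keeps the trial in stage 1, with a 28-day wait after each patient. The other moves it to the CRM stage, where up to two patients may be pending. The patients are under 18 (protocol 6.1.3), and the drug is a T-cell-engaging bispecific antibody. The operating characteristics should show how the chosen rule behaves, but the reader cannot tell which rule Tables 10-12 describe.

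**Working it through.** **Inputs.** True DLT rates are from Table 9. The initial DLT estimates run from 0.001 to 0.50 over 12 levels, the prior on *a* is exponential with mean 1, the target is 0.15, N = 30, and steps are limited to one level (9.1.2.1 and 14.1.1). The rule tested is 14.1.1.2: one patient per level, complete 28-day data, one level up after each patient without a DLT, CRM from the first DLT.

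**Step 1: is Table 11 read correctly?** Table 12 should equal Table 11 x 30 x Table 9.
- Scenario 1, level 4: 0.308 x 30 x 0.15 = 1.39 (1.4 printed).
- Scenario 2, level 8: 0.232 x 30 x 0.15 = 1.04 (1.0 printed).
- Scenario 3, level 12: 0.140 x 30 x 0.10 = 0.42 (0.4 printed).

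The tables agree to within about 0.1, so Table 11 is on a base of 30 patients.

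**Step 2: a floor that needs no CRM model.** Under 14.1.1.2, every trial without a DLT through level 11 treats at least one patient at level 12. In Scenario 2:

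0.999 x 0.995 x 0.99 x 0.98 x 0.97 x 0.95 x 0.90 x 0.85 x 0.75 x 0.65 x 0.55 = 0.1823

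The floor is 0.1823 / 30 = 0.61% of patients, against 0.2% printed. The simulation standard error for 1,000 trials is sqrt(0.1823 x 0.8177 / 1000) / 30 = 0.04 percentage points, so neither noise nor rounding explains the gap. Likewise in Scenario 1, P(no DLT through level 10) = 0.0410, so level 11 holds at least 0.14%, against 0.06% printed.

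**Step 3: level 3 in Scenarios 2 and 3.** Table 11 gives 0.067 x 30 = 2.0 patients. Stage 1 places at most one patient there (0.999 x 0.995 = 0.994 expected, or 3.3%). Only 1 - 0.999 x 0.995 x 0.99 = 1.6% of trials have a stage 1 DLT by level 3. Later returns by the CRM raise the simulated share to about 3.6-4%, not 6.7%.

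**Step 4: Scenario 3, level 12.** P(no DLT through level 11) = 0.6244. If dosing continues at level 12 until a first DLT or patient 30, stage 1 alone places 0.6244 x (1 - 0.9^19) / 0.1 = 5.40 patients there, or 18.0%. This already exceeds the printed 14.0%. The full rule gives about 22-29% by simulation, using posterior mean DLT probability, plug-in of the posterior mean of *a*, posterior median or posterior mode. Stopping once level 12 is reached without a DLT does not restore the table: exposure falls to 4.5%, and level 12 is selected in 61.8% of trials against 39.8% in Table 10.

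**Step 5: selection under the written rule (posterior mean and plug-in).**

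| Scenario, true MTD or top level | 14.1.1.2 rule | Table 10 |
|---|---|---|
| 1, level 4 | 47-50% | 47.2% |
| 2, level 8 | 40-49% | 42.5% |
| 3, level 12 | 39-48% | 39.8% |

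**Step 6: when do the assigned doses differ?** CRM recommendation after one DLT-free patient per level:

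| Levels completed | Posterior mean | Plug-in | Stage 1 next level |
|---|---|---|---|
| 6 | 8 | 9 | 7 |
| 9 | 9 | 10 | 10 |
| 10 | 10 | 10 | 11 |

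After level 6 the one-level limit brings the CRM dose down to 7, the same as in stage 1, so only the wait differs. After level 9 the dose differs under one estimator, and after level 10 under both.

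**The case against.** The strongest reply is that Table 11 is being tested against a rule it never claims to simulate. Section 14.1.1.1 refers to the parameters above it, which means 14.1.1. That section contains both triggers and the two-pending rule, but not the 28-day stage 1 wait, which appears afterwards in an operational section on the dose-allocation module. This stands. A reader might infer that Table 11 is wrong, or that it shows which trigger the sponsor used. The documents support neither. A first-DLT trigger with overlapping stage 1 patients and a Grade 2 trigger with one pending patient each come within about 2 points of Table 11 in all three scenarios, under assumed accrual and Grade 2 rates, and neither matches exactly.

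A reader might also credit the whole Scenario 3 gap to the trigger. That is not supported either. With no pending patients and an assumed Grade 2 rate of 0.3, level 12 takes 24.5% (Grade 2) against 29.4% (first DLT) with plug-in, but 11.5% against 23.0% with posterior mean. The size depends on an estimator that the documents do not name.

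The consequence is also modest. The Scenario 2 gap at the floor is (0.61% - 0.2%) x 30 = 0.12 patients per trial. In Scenario 3, level 12 has a true DLT rate of 0.10, below the 0.15 target, so more patients there is not overdosing. Investigator sign-off, data monitoring committee review and the hold after life-threatening toxicity apply under either trigger, though none of them says when the CRM takes over.

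Two further inferences fail. The statement that the dose-level amendment leaves the operating characteristics unchanged is not shown to be wrong, because Tables 9-12 are indexed by level. The five patients on levels 1 to 4 do not reveal an error in the plan.

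**Conclusion.** The concern holds as a contradictory dosing rule with undocumented operating characteristics, and it should be corrected. The conflict over the trigger is plain from the text and needs no assumption. That Table 11 does not come from 14.1.1.2 rests on the floor of 0.61% against 0.2%, which needs only Table 9, N = 30 and the rule as written. The level 3 figure (about 3.6-4% against 6.7%) and the Scenario 3, level 12 figure (about 22-29% against 14.0%) also rest on a simulated CRM whose estimator had to be assumed.

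Selection of the true MTD is little affected. The main practical effect is on when a second or third patient may be dosed before earlier DLT data are complete. The assigned dose can differ from about level 9. Tables 10-12 are planning figures, since the initial estimates may be revised when the model starts, but they should still describe the rule in use.

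**What to change.** - State one trigger in protocol 4.1.1, 9.1.2.1, 9.1.2.2, 14.1.1 and 14.1.1.2 and in SAP 2.1.1.1, 2.1.1.3, 2.1.1.4 and 2.1.1.5. Either can be defended, and this review does not choose between them.
- State whether stage 1 requires the full 28-day wait or allows up to two pending patients.
- State whether the one-level limit is counted from the last assigned level or from the highest level with complete data.
- Re-run the 1,000-trial simulation under that exact rule, giving the CRM estimator and accrual rate, and the Grade 2 or higher rates if that trigger is kept. Replace Tables 10-12.

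The cost is a wording amendment and a few hours of simulation, with no extra patients. If the first-DLT trigger and the stage 1 wait are both kept, the stated exposure at Scenario 3, level 12 would rise from 14.0% to about 22-29%.
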